9.1.2 Concomitant Medications

Concomitant medications will be managed by the treating neuro-oncologist and recorded at each study visit by the study team.

9.2 Rationale for Selection of Dose, Regimen, and Treatment Duration

The PEP_{IDH1M} vaccine dose that will be evaluated in this trial will be 500 µg with 150 µg of GM-CSF mixed 1:1 with Montanide ISA 51 administered intradermally as vaccine # 1. Subsequent vaccines will be given on day 15 ±3 days (vaccine #2) and on day 29 ±3 days (vaccine #3). The same dose will be administered on day 22 (+ 2 days) of each monthly cycle of adjuvant TMZ following surgical resection for those with confirmed Grade II. For those who transition to a higher grade glioma, they will be undergoing RT (please see Section 18.4 in the Appendices for SOC RT), thus, vaccine #4 will be given during SOC clinic visit prior to initiating RT, and vaccine # 5 will be given 4 weeks later (± 1 week) during RT. Vaccine #6 will be given at the end of RT during the SOC clinic visit to review MRI and begin post-RT TMZ, if MRI stable. Then, subjects in this treatment group will receive vaccines monthly on day 22 (+ 2 days) with post-RT cycles of TMZ to a maximum of 15 vaccines, as the confirmed Grade IIs.

The nearly universal expression of IDH1 in secondary GBMs and low-grade gliomas may make excellent anti-tumor immunotherapeutic targets. Vaccination and adoptive T-cell strategies in humans in other contexts have been safe and effective. Therapeutic TMZ induces a profound lymphopenia that may enhance anti-tumor vaccination responses when given during the homeostatic T-cell proliferation that occurs in response to lymphodepletion. Other peptide vaccines given to patients with high-grade gliomas during recovery from TMZ-induced lymphopenia have produced potent tumor-specific immune responses and have been well tolerated^{9,17,81}.

9.3 Rationale for Correlative Studies

While the primary goal of this study is to assess safety of the PEP_{IDH1M} vaccine, a secondary endpoint will be to determine whether this vaccine is capable of eliciting an immune response in patients with IDH1 mutation-expressing tumor. The primary measure of immunogenicity will be by ELISpot to the immunizing peptide. For the immune system to recognize the tumor specific IDH1 mutant, this mutant peptide must be presented by human leukocyte antigens (HLA) on the surface of a tumor cell for recognition by a T cell. There are a tremendous number of HLA alleles with variable expression from person to person. As certain peptides are able to bind with much greater affinity to certain HLA alleles, the ability of one individual to present the IDH1 mutant peptide will be dependent upon their unique set of HLA alleles and may differ greatly from another individual with differing HLA. Therefore, it is critical to know the HLA type of a patient receiving the peptide vaccine as this may reveal if certain HLA types are associated with enhanced vaccine induced immune responses. Such information may suggest certain HLA types present the mutant peptide in a superior fashion and may be valuable in stratifying patients for clinical trials using this vaccine. We

intend to identify HLA types from PBMCs taken at the leukapheresis time point. The purpose of collecting these data will be to determine whether there may be immune correlates that associate with clinical outcomes such as PFS and OS following vaccination with the PEP_{IDH1M} vaccine. Although this Phase I study is not designed to be definitive towards this end, these analyses will provide the initial data necessary to adequately power future studies. Any evidence of tumor response will be determined according to the Duke PRTBTC SOP (available upon request). RANO criteria⁸² will be used for assessment of pseudoprogression. Tumor progression will need to be documented histologically, unless there are clinical contraindications, to exclude inflammatory responses presenting as radiographic or clinical changes, which could indicate potentially toxic or therapeutic responses and not tumor progression. Patients will be followed until death.

9.4 Rationale for Genomic Proteomic Analyses

IDH1 mutation is a critical factor in glioma classification and a key determinant of clinical outcome. First, though the effect of mutant IDH1 in tumor cells have been well-established at the genetic and epigenetic levels (e.g., closely associated with several other genes, and has a profound impact in DNA methylome), the effect of the IDH1 mutant on the proteomic level is unclear, thus presenting a great opportunity for understanding glioma pathogenesis and developing new therapeutics. Second, in addition to IDH1 mutations, other genetic alterations and their associated mutant peptides may serve as multi variant factors underlying patient treatment outcome. It is critical to have a bird's eye view of and dissect all the genetic and peptide components that help stratify patients for clinical trials.

We intend to identify genetic alterations, differential protein expressions or post-translational modifications (PTMs) via our comprehensive 'inside-out' quantitative proteomic strategies in patient-derived tumor samples. Genetic alterations, differential protein expressions or PTMs that have been identified will be further tested in all patients enrolled in this clinical trial. We propose to obtain the following specimens, from patients both before and after treatment, for both genomic and proteomic analyses.

- (1) Tumor tissues 500 mg fresh frozen tumor tissue will be requested, as well as tissues from previous surgery. If frozen tissues from previous surgery are not available, fifteen 5 µm sections of FFPE samples are requested. If available, these samples will be used for genomic and proteomic analysis.
- (2) PBCs to determine proteomic profiling with a focus on immune system, and also for immune monitoring and tumor circulating DNA detection. Twenty mLs of peripheral blood (3 yellow top tubes) is requested (1) before vaccine with the leukapheresis visit, (2) at the pre-op screening visit before surgery, (3) At the SOC clinic visit prior to starting the 1st cycle of TMZ for those who are confirmed Grade II, or at the SOC clinic visit prior to starting RT/TMZ for those who have transitioned to a higher grade glioma, (4) Vaccine #6, and (5) End of Treatment (follow-up visit 1 month after vaccine #15). If a subject decides to stop participating in the study prior to vaccine #15, blood will be obtained at that time (if possible). If a subject progresses prior to vaccine #15, blood will be obtained at that time (if possible). PBMCs and plasma will be separated. Plasma will used for the detection of IDH1 mutation before surgery.

These experiments will:

- Identify genetic alterations and changes in protein before and after treatment with peptide vaccine in tumor cells.
- Identify proteins showing differential expressions or PTMs in immune cells, with and without IDH1 mutant, and before and after IDH1 vaccination, with a potential of revealing how immune cells response to IDH1 mutant, before and following vaccination.

We will perform proteomics, exome sequencing and RNA-sequencing on the resected tumors (after three IDH1 vaccines). We will use patient samples before IDH1 vaccination as controls. Radiographic and clinical tumor progress, as well as IDH1 mutation status in patient's plasma will be recorded.

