We plan to isolate circulating nucleic acids from the plasma of patients affected by glioma and attempt to detect tumor-specific circulating DNA containing the c.395G>A (R132H) mutation. We will follow the protocol as described by Boisselier, et al., Neurology 2012⁸³ for plasma collection. Twenty mLs of blood will be the appropriate amount for our analyses (should yield ~10mL of plasma). At the same time, we will collect peripheral blood for immune monitoring. Ideally, we would like to have these blood samples collected:

- (1) Prior to initiating vaccine therapy at the leukapheresis visit,
- (2) Prior to surgical resection at the pre-op screening visit,
- (3) Prior to first cycle of TMZ at the SOC clinic visit (confirmed Grade IIs), or prior to RT/TMZ at SOC clinic visit (higher Grade Gliomas),
- (4) Vaccine #6
- (5) End of Treatment (follow-up visit 1 month after vaccine #15). If a subject decides to stop participating in the study prior to vaccine #15, blood will be obtained at that time (if possible). If a subject progresses prior to vaccine #15, blood will be obtained at that time (if possible).

b) Study of 2-Hydroxyglutarate levels in patients with gliomas with IDH1 R132H:

The second approach to be used will be a mass spectrometry-based approach for detection of 2hydroxyglutarate (2-HG), a metabolite specifically produced by tumors with the IDH1 c.395G>A (R132H) mutation. This metabolite can be sensitively detected by mass spectrometry and has been found to be elevated in the tissue of IDH1 R132H-containing gliomas as well as in the plasma of other solid tumors containing the same mutation (cholangiocarcinoma, subsets of breast carcinoma). A small portion of the previously mentioned isolated plasma will be used for a LC-MS/MS based approach for sensitive detection of circulating 2-HG levels.

Tumor tissue – we are planning to obtain a snap-frozen tumor tissue sample after the surgical resection for possible presence of IDH1 mutation and gene up-regulation.

Tumor Sampling Analyses:

At the time of surgical resection, excess tumor tissue will be obtained through the Duke Biorepository, and IHC analyses will be performed to assess immunologic infiltrate which will be identified by cell type and reactivity state.

Table 2. Screening and On-Study Tests and Procedures

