- 7. Genomic and proteomic analyses of the pre-treatment pathologic specimen and the post-vaccination surgical sample will be conducted. Changes in genetic alterations, differential protein expressions and PTMs will be described. If statistical tests are conducted, appropriate adjustment for multiplicity will be considered.
- Measures of metabolism in IDH1+ gliomas will be assessed at several time points. Paired comparison (e.g. paired t-tests) will be used to assess whether same-day measures on a patient are the same. Assuming repeatability, changes over time in levels of metabolism will be described.

Additional exploratory analyses may be conducted. Among these additional exploratory analyses will be an examination of the relationship among changes in metabolism, genomic expression, 2-HG metabolite, and pathologic expression of IDH.

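### Where only FFPE tissue survives from the earlier surgery, the before/after tumour comparison sets FFPE against frozen, so a tissue-handling difference could be read as change after vaccination

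*Combined protocol and SAP*

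**What the plan says.** The relevant text lies in Table 1 and Sections 9.4, 12 and 15.6 of the combined protocol and SAP.

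- **After sample.** Section 9.4: "500 mg fresh frozen tumor tissue will be requested, as well as tissues from previous surgery". Section 12 agrees: "we are planning to obtain a snap-frozen tumor tissue sample after the surgical resection". Section 9.4 names the assays: "We will perform proteomics, exome sequencing and RNA-sequencing on the resected tumors (after three IDH1 vaccines").
- **Before sample.** Tissue from the previous surgery. The fallback is conditional: "If frozen tissues from previous surgery are not available", fifteen "sections of FFPE samples are requested". It is given for previous-surgery tissue only.
- **Use of both.** "If available, these samples will be used for genomic and proteomic analysis". No assay is reserved for one type of preservation.
- **Comparison.** Section 9.4: "We will use patient samples before IDH1 vaccination as controls". Section 15.6: "Genomic and proteomic analyses of the pre-treatment pathologic specimen and the post-vaccination surgical sample will be conducted". Table 1 sets the endpoint as the change from baseline to surgery in genetic alterations, protein expression and PTMs, under an objective about the impact of vaccination.
- **Safeguard.** Section 15.6 will describe the changes. If tests are run, a multiplicity adjustment will be considered. Nothing is said about preservation type.

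**The concern.** The fallback works in one direction only. A mixed pair is always FFPE before and frozen after, never the reverse. Within mixed pairs, preservation type and time point are therefore the same variable. A systematic difference between FFPE and frozen material has the same sign in every such pair and does not average out as more patients are added.

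A multiplicity adjustment guards against chance findings and leaves a biased mean difference where it is. Descriptive reporting does not help either, because the described mean change carries the same bias.

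What is at stake is the list of features that this exploratory work puts forward. Section 9.4 says that alterations identified in tumour samples will be tested further in all enrolled patients, and it hopes that such features will help to stratify patients in trials. Section 15.6 also plans to relate genomic expression to metabolism, the 2-HG metabolite and IDH expression. A handling artefact could travel into each of these.

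**Working it through.** The documents give no sample size, power or error rate for this comparison, so there is no figure to reproduce. The check has two parts.

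**1. Which pairings the text allows**

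| Tissue kept from previous surgery | Before | After | Preservation aligned with time? |
|---|---|---|---|
| Frozen available | Frozen | Frozen | No |
| Frozen not available, FFPE available | FFPE | Frozen | Yes, fully |
| Neither | none | Frozen | No pair |

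The second row is permitted by 9.4. No section routes it to a separate analysis.

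**2. How an offset would act**

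For one feature, let the after-minus-before difference in patient *i* be

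D_i = V + b·F_i + e_i,

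where V is the true change, b the FFPE-versus-frozen offset, F_i = 1 for a mixed pair and 0 for a frozen-frozen pair, and e_i has SD 1. With m mixed pairs among n, the mean difference has expectation V + b·(m/n).

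Inputs:
- V = 0, to see what appears when nothing has changed.
- n = 20. This borrows the target in 15.4.2 for patients with at least 6 vaccines. It is not a count of tissue pairs, which the documents do not give.
- m and b are assumptions, shown as a range, because the documents give neither.
- Test: two-sided 5% paired t-test with no multiplicity adjustment. This is an illustration; 15.6 does not specify it.

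Simulated share of affected features declared changed (100,000 runs per row):

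| Mixed pairs (of 20) | Offset b (SD) | Mean shift b·m/n | All pairs combined | Frozen-frozen pairs only |
|---|---|---|---|---|
| 5 | 0.5 | 0.125 | 8% | 5% |
| 5 | 1 | 0.25 | 14% | 5% |
| 5 | 2 | 0.5 | 31% | 5% |
| 10 | 0.5 | 0.25 | 17% | 5% |
| 10 | 1 | 0.5 | 47% | 5% |
| 10 | 2 | 1.0 | 92% | 5% |
| 20 | 0.5 | 0.5 | 56% | no such pairs |
| 20 | 1 | 1.0 | 99% | no such pairs |

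For the same mean shift, a part-mixed set rejects less often than an all-mixed one (92% against 99% at a shift of 1.0). Mixing the pair types adds b²·(m/n)(1 − m/n) to the variance: with b = 2 and m/n = 0.5 that is 4 × 0.25 = 1, so the SD rises from 1 to √2.

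**With a multiplicity adjustment.** Take 10 mixed pairs and a Bonferroni threshold for an assumed 100 features, which is 0.05/100 = 0.05% per feature. The rates for offsets of 0.5, 1 and 2 SD become about 0.5%, 2.5% and 13%. These are far below the unadjusted figures, yet about 10, 50 and 260 times the 0.05% intended. The mean shift itself is unchanged.

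**The case against.** Several points on the other side are sound.

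- **The plan does not say that all pairs are pooled.** A reader might infer a single combined estimate from 9.4 and 15.6. Neither section mentions one; 15.6 says only that changes will be described. What stands is narrower: the plan allows mixed pairs into the comparison and gives no rule for them.
- **The offset is not always inseparable.** A reader might infer that the trial could not tell handling from biology. Preservation type can be known for each sample, and where some pairs are frozen-frozen a restricted or stratified summary is open to the analyst; the table shows that it keeps 5%. Only if every earlier sample is FFPE is there no such route. The cost of restricting is fewer pairs.
- **The percentages are not the plan's error rates.** They are unadjusted and rest on an assumed offset, SD, FFPE share and number of pairs.
- **Matching would not isolate a vaccine effect.** The earlier tissue comes from another operation, patients enter with progressive disease, and some tumours will have moved to a higher grade. Those differences belong to the design. The handling difference is a matter of specimen choice and can be removed.
- **FFPE is a sensible fallback.** It avoids losing the patient's baseline, and laboratory procedures in separate documents may cover handling. Nothing in the protocol or SAP says that they do.
- **The endpoint is exploratory**, with no hypothesis or decision attached. That limits the weight of the point, but the correction is small as well.

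**Conclusion.** The point holds in limited form. In patients whose earlier tissue exists only as FFPE, preservation type is fully aligned with before/after, and the plan has no rule to keep an FFPE-versus-frozen offset out of the reported change. Such an offset could be read as change after vaccination; the documents do not support saying that it would be, because the share of these patients and the size and direction of the offset are not stated. Nor need the offset be equal across assays.

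The bias in a combined mean is the offset times the share of mixed pairs. Under the assumptions above, with half of 20 pairs mixed, that gives a false change in about 17%, 47% or 92% of affected features for offsets of 0.5, 1 or 2 SD, against 5% in frozen-frozen pairs alone.

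The primary safety analysis and the secondary ELISpot analysis do not use these samples and are unaffected. This is a cheap improvement to one exploratory endpoint.

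**What to change.** In Section 9.4:
- Record the preservation type of every tumour sample.
- Where the earlier tissue is FFPE, also take FFPE sections of the study-surgery tumour and compare FFPE with FFPE.

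In Section 15.6:
- Report frozen-frozen and FFPE-FFPE pairs separately, and do not combine mixed pairs with either.
- State that matching removes only the handling artefact. Elapsed time, progression and interval treatment still separate the two samples, so a change should not be attributed to the vaccine alone.

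Cost: a few extra sections from tumour that is already resected and graded at study surgery, and wording in two sections. This assumes that FFPE material from that operation can be released for research, which the documents do not state and the sponsor should confirm. Treatment, visits and sample size do not change. The downside is fewer pairs in each comparison, and some assays limited to what FFPE supports.

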9.5 Single-Voxel MR Spectroscopy

To demonstrate quantitative repeatable measures of metabolism change in IDH1+ gliomas, patients will be scanned on the research MR scanner using standardized MRS protocol to assess same-day repeatability and to assess longitudinal metabolite changes.

The IDH1 mutation causes extreme overexpression of the onco-metabolite R-2-hydroxyglutarate (2HG) in all tumor cells. This can be non-invasively measured using clinical MRS methods. 2HG is a specific marker for IDH1 mutated gliomas because its concentration in 'wild' IDH1 gliomas is below the level of measurement of MRS.

Duke Radiology has a standard protocol for 2HG measures using a proven 2HG MEGA-LASER pulse sequence for Siemens MR scanners and [name] open source "Vespa" software for spectral simulation and fitting of the MEGA-LASER data. The protocol is available for immediate use on our research scanner as a part of the Duke Radiology's Center for Advanced MR Development (CAMRD).

We will assess subjects at up to 5 time points: baseline (after consent and before PEP_{IDH1M} vaccine #1), and up to 4 times prior to surgery. This will provide between 6-8 weeks of tumor/vaccine interaction. A typical 2HG protocol consists of 12-15 minutes of anatomical MRI and ~15-30 minutes of MRS data acquisition. An IDH1+ patient can usually be processed in a 1-2 hour time slot.

In order to establish same-day coefficients of variance and/or optimized acquisition parameters, patients may be scanned twice within a time point. Patients will be positioned and scanned in the MR scanner, then completely removed and put back into the scanner, and then positioned and scanned a second time. If necessary for patient comfort, this evolution can be done immediately or with a short rest period so long as scanning is finished within the booked period of time. Longitudinal acquisitions will also be analyzed for longitudinal metabolite coefficients of variance and possible longitudinal metabolite changes.

9.6 Definition of Evaluable Subjects, On Study, and End of Study

For the initial monitoring of adverse events (see Section 15.4.2), evaluable patients will include the first 6 accrued patients who received 3 vaccinations or experienced an unacceptable toxicity due to one of the first 3 vaccinations.

For the final analysis of the primary objective (See section 15.4.2), evaluable patients will include all patients who received at least 6 vaccinations or experienced an unacceptable adverse event that was related to vaccine (or vaccine + TMZ).

Once the patient signs ICF, that subject will be considered "on study." Rationale for taking patient off protocol treatment will be documented. End of study is defined as 2 months following last vaccine for purposes of toxicity monitoring.

9.7 Early Study Termination

This study can be terminated at any time for any reason by the PI-sponsor. If this occurs, all subjects on study should be notified as soon as possible. Additional procedures and/or follow up should occur in accordance with Section 12.5. Section 12.6 describes procedures and process for prematurely withdrawn patients.

10STUDY DRUG

10.1 Names, Classification, and Mechanism of Action

The name of the drug will be $\mathsf{PEP}_{\mathsf{IDH1M}}$ vaccine. The class of action is a biological.

10.2 Packaging and Labeling

Name MRN DOB Drug: PEP_{IDH1M} Lot #: Lot 001 Caution New Drug Limited By Federal Law To Investigational Use

10.3 Supply, Receipt, and Storage

The PEP_{IDH1M} will be manufactured under GMP conditions by Bachem Americas, Inc., and stored in the investigational pharmacy. Montanide is supplied by Seppic and stored at 4°C in the investigational pharmacy.

GM-CSF (LEUKINE®; sargramostim) will be obtained from commercial supply, as a sterile, white, preservative-free powder lyophilized powder in a vial containing 250 mcg to be reconstituted in 0.5 mL of sterile water for injection.

Store GM-CSF under refrigeration at 2-8°C (36-46°F). Vials must not be frozen.

Lyophilized GM-CSF vials contain no antibacterial preservative, and therefore solutions prepared with Sterile Water for Injection, USP should be administered as soon as possible, and within 6 hours following reconstitution. The vial should not be re-entered or reused. Do not save any unused portion for administration more than 6 hours following reconstitution. Bacteriostatic Water for Injection, USP (0.9% benzyl alcohol) should NOT be used.

Aseptic technique should be employed in the preparation of all GM-CSF solutions. To assure correct concentration following reconstitution, care should be exercised to eliminate any air bubbles from the needle hub of the syringe used to prepare the diluent. During reconstitution of lyophilized GM-CSF, the diluent should be directed at the side of the vial and the contents gently swirled to avoid foaming during dissolution.

PEP_{IDH1M} will be stored at -80°C, thawed, and inspected visually for particulate matter and discoloration prior to administration. If particulate matter is present or the solution is discolored, the vial should not be used. Before use, the vial should be gently swirled to ensure uniform mixing of the contents. Avoid excessive or vigorous agitation; do not shake.

Td is indicated for active booster immunization against tetanus, diphtheria, and pertussis as a single dose; substitute 1-time dose of Tdap for Td booster, then standardly boost with Td every 10 years. Please refer to section 7.2 on the use of Td in this protocol. This study agent Td (Tetanus diphtheria toxoid adsorbed) is supplied by Duke Pharmacy and stored at 4°C.

